2.4.6.3 Primary Outcome Measures

The primary endpoint of the feasibility study is the use of external abdominal wall fetal ECG sensors to assess FHR; its use-friendliness, the signal-noise ratio and the correlation with acoustic data.

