1. SYNOPSIS

| | |
|---|--|
| Study Title | Intraoperative fetal heart rate (FHR) monitoring: a Feasibility Study |
| Objective | The introduction of intraoperative fetal heart rate (FHR) monitoring; demonstrating that intraoperative FHR monitoring is technically feasible. |
| Study Period | Planned enrollment duration: 6 months Planned study duration: 6 months |
| Number of Patients | 55 patients |
| Study Treatment | |
| Study Design | Observational Study |
| Inclusion and Exclusion Criteria | 
Inclusion Criteria:
 
 1. First 15 patients only— Elective induction of labor, not yet in active labor. 2. Subsequent 40 patient – Scheduled cesarean sections performed under spinal anesthesia 3. Patients ages 18-45 
Exclusion Criteria
 
 1. Urgent or emergent cesarean sections 2. Cesarean sections performed under general anesthesia |
| Statistical Methodology | Demographic, clinical characteristics will be summarized using descriptive statistics |

CONFIDENTIAL: This document is the intellectual property of [name]. Acceptance of this document constitutes the agreement by the recipient that no unpublished information contained herein will be published or disclosed without prior written approval.

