2.2 Objective

The first objective of this study is the introduction of intraoperative fetal heart rate (FHR) monitoring as a novel fetal endpoint to be utilized in scheduled and urgent cesarean deliveries, in order to shed important light on the immediate fetal responses to maternal anesthetic and obstetric interventions. This research is intended to demonstrate that intraoperative FHR monitoring is technically feasible, and correlates with other traditional endpoints of immediate neonatal wellbeing (such as umbilical arterial blood gas analysis and Apgar score). Unlike these post-delivery neonatal outcomes, intraoperative FHR monitoring has the potential to serve as a real-time target for optimization of maternal and fetal condition in order to improve immediate neonatal outcome. We will first assess the fetal ECG monitors on a pilot of 15 patients for induction of labor who are not yet in active labor or in pain; the aim being to determine the best placement of the ECG leads. We will then assess the technical feasibility of intraoperative FHR monitoring using both the standard abdominal wall acoustic device used routinely in labor and a series of multiple ECG leads placed over the upper abdominal wall.

CONFIDENTIAL: This document is the intellectual property of [name]. Acceptance of this document constitutes the agreement by the recipient that no unpublished information contained herein will be published or disclosed without prior written approval.

DoCTR

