2.4.6 Observations and Measurements

This will be an observational study. We will first assess the fetal ECG monitors on a pilot group of patients for induction of labor who are not yet in active labor or in pain. We will then assess the technical feasibility of intraoperative FHR monitoring. Fetal heart rate will be assessed by:

a) External abdominal wall fetal ECG sensors placed at the top of the belly, outside the sterile field, or on the participant's back. This data is captured via BioSemi FLAT Active electrodes that interface with an ECG system that employs the algorithm ActiView to analyze the data. [See Appendix A].

[figure not shown]
b) An acoustic fetal heart sensor, as used routinely in labor will be used as a comparator in this feasibility study. When this device is used intraoperatively, sterility and acoustic contact are both maintained by placing the acoustic probe inside a sterile nylon sleeve containing electrode gel, and by using sterile electrode gel between the sterile sleeve and the abdominal wall. This technique may require the presence of an investigator "scrubbed into" the case to hold the abdominal wall probe (ie surgical scrub, sterile gown and gloves). This will be decided on a case-by-case basis. If needed, this investigator will need acoustic input to ensure adequate contact. So as not to distract the surgeon, this will be transmitted to the investigator by earphone input. These are scheduled cesarean deliveries and no fetal heart rate anomalies are expected; if there is an unexpected fetal bradycardia, this will be communicated to the surgeon.

c) Routine maternal vital signs (heart rate, blood pressure and oxygen saturation).

Group 1 – Patients for elective induction – not in active labor

- a) We will use the routine acoustic fetal heart rate sensor and try to determine the best placement of external abdominal wall fetal ECG sensors (either at the top of the belly outside the sterile field, or on the participant's back)
- b) We aim to capture 10 minutes of FHR with the ECG sensors comparing it to the acoustic monitor
- c) We will start with 5 patients. If we are able to capture FHR for the allotted period of time with the fetal ECG, then we will proceed to the intraoperative group. If not, we will assess another 5 elective induction patients.
- d) We will plan for an upper limit of 15 patients in this group

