CONFIDENTIAL: This document is the intellectual property of [name]. Acceptance of this document constitutes the agreement by the recipient that no unpublished information contained herein will be published or disclosed without prior written approval.

Group 2 – Patients for scheduled cesarean section

- a) We will use the acoustic FHR sensor and the fetal ECG sensors.
- b) We will start with 5 patients and determine if we can capture fetal ECG. If this information correlates with the acoustic FHR, we then use only the fetal ECG sensors for the remaining 35 patients. We will adjust placement of leads for each group of 5 patient if there proves to be difficulty with capturing FHR intraoperatively, though all leads will be placed on the belly outside the sterile field or on the participant's back
- c) We will plan for an upper limit of 40 patients in this group

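### Intraoperative feasibility is not measured as readable FHR time, and no operative result is named in advance as supporting or refuting it

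*Combined protocol and SAP*

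**What the plan says.** The Synopsis gives the objective as "demonstrating that intraoperative FHR monitoring is technically feasible", and section 2.2 repeats it: "This research is intended to demonstrate that intraoperative FHR monitoring is technically feasible". Section 2.1 explains the need: between induction of anesthesia and delivery there is no real-time information on the fetus.

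Section 2.4.6.3 makes the primary endpoint the use of external ECG sensors to assess FHR, and then lists what is to be looked at: "its use-friendliness, the signal-noise ratio and the correlation with acoustic data". It gives no unit, time window, denominator or threshold.

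Capture appears in section 2.4.6. For Group 1 (elective induction, not in surgery): "We aim to capture 10 minutes of FHR with the ECG sensors comparing it to the acoustic monitor". Then: "If we are able to capture FHR for the allotted period of time with the fetal ECG, then we will proceed to the intraoperative group". And: "If not, we will assess another 5 elective induction patients". The ceiling is set by "We will plan for an upper limit of 15 patients in this group".

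For Group 2 (cesarean), the first 5 patients have both devices, and the investigators see whether fetal ECG can be captured. If it correlates with the acoustic signal, the remaining 35 have ECG only. If capture is difficult, leads are moved between blocks of 5. The ceiling is "We will plan for an upper limit of 40 patients in this group".

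Section 2.4.6.4 describes a silent period, from removal of the routine monitor to delivery, but uses it only for the secondary endpoint. Section 2.4.6.5 plans descriptive statistics and an ROC curve. Section 2.4.6.6 gives the sample size as 55, without a derivation.

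**The concern.** For a monitor meant to fill a gap in surveillance, the first feasibility question is how much of the gap it fills, and in how many patients. The plan does not define that quantity for the operating room.

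Of the three listed attributes, correlation comes closest, but it is blind to lost signal: a minute without an ECG reading contributes no pair. It may also be available for only a few of the cesareans. Signal-noise ratio bears on readability, but without a cut-off and a time base it does not give readable minutes. Ease of use does not give them either.

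Two things are at stake. First, the report could show good agreement while most of the operative window was unread. Second, intermediate results, where a rule matters most, would be judged feasible or not after the data are seen. The secondary endpoint inherits the problem, because an unreadable minute looks the same as a minute without a non-reassuring pattern.

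**Working it through.** **1. The plan's own figure.** 15 + 40 = 55, which agrees with section 2.4.6.6. Nothing further can be reproduced: no success rate, precision target, alpha or power is given.

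**2. Where a capture criterion exists.**

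| Place | Setting | Capture criterion | If not met |
|---|---|---|---|
| 2.4.6, Group 1 | Not in surgery | 10 minutes, worded as an aim; number of the 5 needed not stated | 5 more patients, up to 15; conclusion after 15 not stated |
| 2.4.6, Group 2 | Cesarean | Whether ECG can be captured; no duration or proportion | Leads moved, up to 40; conclusion not stated |
| 2.4.6.3 | Primary endpoint | None quantified | None |
| 2.4.6.5 | Analysis | None | None |

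**3. Reach of the correlation.** If the acoustic device is dropped after the first 5 cesareans, paired data exist for 5/40 = 12.5% of Group 2 and are absent for 35/40 = 87.5%. Within those 5, only jointly readable moments count. Illustration with assumed figures: an ECG readable for 20% of the window with r = 0.95 in that time gives a reported correlation of 0.95. The unread 80% does not enter it.

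**4. Effect on the secondary endpoint.** Assume that 10 of 40 patients have one brief non-reassuring pattern, that it falls at random in the window, and that 20% of the window is readable. Expected patterns seen: 10 × 0.20 = 2. The reported incidence would be 2/40 = 5% against a true 10/40 = 25%. The report could not show the difference without readable time as the denominator.

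**5. How much the unstated Group 1 count matters.** Let p be the true per-patient capture rate (assumed) and r the number of 5 required. A block passes with probability P = Pr(Bin(5, p) ≥ r). The chance of passing within three blocks is 1 − (1 − P)³.

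| p | r = 1 | r = 3 | r = 5 |
|---|---|---|---|
| 20% | 0.965 | 0.164 | 0.001 |
| 50% | above 0.99 | 0.875 | 0.091 |
| 80% | above 0.99 | above 0.99 | 0.696 |

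At p = 50%, whether the study moves to surgery is nearly certain or unlikely, depending on a number that the plan does not state.

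**6. What the planned numbers could support.** Suppose each cesarean patient were scored as reaching or not reaching a fixed readable percentage. Exact (Clopper-Pearson) 95% intervals with n = 40:

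- 20/40: 33.8% to 66.2%
- 28/40: 53.5% to 83.4%
- 36/40: 76.3% to 97.2%

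The lower limit first exceeds 50% at 27/40 (50.9%; 26/40 gives 48.3%). For one block of 5 with all successes, the lower limit is 0.025^(1/5) = 47.8%. So 40 patients give a usable estimate if placement is stable, and a single block gives a weak one.

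**7. Why a pooled count would not serve as the rule.** Leads may move between blocks. Assume 30% success in the first 20 patients and 90% in the last 20. The expected total is 20 × 0.30 + 20 × 0.90 = 6 + 18 = 24, and the chance of reaching 27/40 is about 15%, although the final placement works well. Even with a constant rate, 27/40 is reached with probability 0.44 at a true 65% and 0.70 at a true 70%.

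**The case against.** The strongest reply is that capture is not absent from the plan. The endpoint's opening clause, use of the sensors to assess FHR, is naturally read as a capture question. Group 1 has a 10-minute target, and entry to surgery is conditional on it, so on a literal reading 15 failures mean that Group 2 does not open. This is also a first, observational, descriptive study with no preliminary data (section 2.1.1), for which a formal hypothesis test is not required.

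Most of this stands, and it limits the point. The defect is that intraoperative capture is not defined or given a criterion; it would be wrong to say that the plan ignores capture. Three stronger readings are tempting, and the documents do not support them:

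- A reader might infer that the study cannot show feasibility either way. Descriptive data could still make near-total success or failure plain.
- A reader might infer that a sensor readable for 20% of the time would satisfy every component of the endpoint. No component has a threshold, so nothing satisfies it. Signal-noise ratio might be computed over the whole recording and worsen in unreadable stretches; its time base is not stated.
- A reader might infer that the patient limits have no consequence. Group 1 does gate Group 2. What is missing is the number of the 5 required and the conclusion to report if the gate is never passed.

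What the reply does not answer is that the Group 1 target is non-operative and outside the primary endpoint, and that a study meant to demonstrate feasibility should say beforehand which operative result would do so.

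**Conclusion.** The concern holds in this limited form. The primary endpoint names use of the ECG sensors but does not define the share of the intraoperative period, or the number of patients, with a readable FHR. No prespecified operative result would support or refute feasibility. Correlation cannot stand in, because it omits lost signal and may cover only 5 of 40 cesareans. The incidence of non-reassuring patterns cannot be interpreted without readable time.

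The size of any distortion cannot be derived from the documents, which give no expected capture rate. The 20% readable time, the capture rates and the 27/40 count above are illustrations. The conclusion rests on the text; figures not reproduced there could not be checked. This goes beyond missing detail, since a better measure is available from recordings already planned. It is an inexpensive improvement, best made before data are seen.

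**What to change.** - **Primary measure (2.4.6.3).** For every Group 2 patient in whom ECG capture is attempted, use the percentage of the silent period of 2.4.6.4 with an interpretable ECG-derived FHR. Fix the reading rule in advance, record the start and delivery times, and count a patient with no signal as 0%.
- **Reporting (2.4.6.5).** Give the distribution of this percentage, and the proportion of patients reaching a level that the investigators fix in advance, with an exact 95% interval on the number actually studied (40 is an upper limit). Show it overall and by lead placement, with the final placement separate.
- **Decision.** State in advance which result for the final placement will be called feasible and which will not. Values such as 80% readable time or a 50% lower limit are examples only; the investigators must choose and justify their own.
- **Group 1.** State how many of 5 must reach the 10-minute target. If no block meets the target, report the result as not feasible with the placements tried.
- **Supporting measures.** Keep signal-noise ratio, ease of use and the device comparison. Report non-reassuring patterns against readable time.

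**Cost.** No added patients or recordings, but a reading rule, time stamps and some analysis work. Precision by placement will be low (5/5 still gives 47.8% to 100%), and the study can then return a negative answer.

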2.4.6.4 Secondary Outcome Measures

Secondary endpoints are the incidence of any non-reassuring FHR patterns during the "silent" period which is the period when the FHR monitor is removed, the patient's abdomen is scrubbed, sterile prep and drape until delivery of the fetus. If there are any non-reassuring FHR patterns (tachycardia, bradycardia, decelerations), maternal vital signs at the time will be noted.

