2.4.6.5 Statistical Methods

Demographic and clinical characteristics will be summarized using descriptive statistics; FHR data will be compared for the two tests using Receiver Operating Characteristic or ROC curve.

[figure not shown]

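### The device comparison has no patient level and no within-fetus measure, so a pooled correlation could look substantial when the ECG follows no change within a fetus

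*Combined protocol and SAP*

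**What the plan says.** Section 2.4.6.3 defines the primary endpoint as use of the fetal ECG sensors to assess FHR: "its use-friendliness, the signal-noise ratio and the correlation with acoustic data". The element at issue here is "the correlation with acoustic data". For the analysis, section 2.4.6.5 offers descriptive statistics for demographic and clinical characteristics, and for the devices this: "FHR data will be compared for the two tests using Receiver Operating Characteristic or ROC curve".

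The data are repeated within patient. For Group 1 (5 to 15 women), section 2.4.6 states: "We aim to capture 10 minutes of FHR with the ECG sensors comparing it to the acoustic monitor". In Group 2 both devices are used on the first five cesarean patients, and item (b) sets the rule: "If this information correlates with the acoustic FHR, we then use only the fetal ECG sensors for the remaining 35 patients".

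The secondary endpoint in 2.4.6.4 is the "incidence of any non-reassuring FHR patterns" during the period when routine monitoring is off. Tachycardia, bradycardia and decelerations are its examples.

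The documents do not give a reading interval or epoch, a unit of analysis, a patient term, an agreement measure, a confidence interval, or a cut-off for what counts as correlating.

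**The concern.** A correlation over repeated readings mixes two questions. One is whether the ECG ranks fetuses by baseline rate in the same order as the acoustic sensor. The other is whether the ECG rises and falls with the acoustic trace inside one fetus. The secondary endpoint depends on the second, since a deceleration is a change within a fetus.

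There are two obvious ways to obtain a single coefficient, and neither isolates that question. Pooling all readings lets baseline differences between fetuses into the coefficient and treats dependent readings as independent. Using one value per patient removes the counting problem but leaves only between-fetus association.

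At stake is the five-patient decision in Group 2. If it passes, the next 35 cesarean patients have no acoustic comparator, so a failure to track could not be found afterwards, and the pattern endpoint in those patients rests on the ECG alone.

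**Working it through.** **Inputs from the documents.** The total of 55 is 15 + 40, and Group 2 is 5 + 35 = 40. No power, precision or target correlation is attached, so these figures can be checked only as sums. If the Group 2 decision passes at its first look, paired data come from 5 + 5 = 10 to 15 + 5 = 20 women. If it does not pass, paired use could go on and the number could be larger.

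**Assumptions (the documents give none of these).** Between-fetus SD 10 bpm, so variance B = 100. Within-fetus SD 6 bpm, so variance W = 36. Number of readings per patient and intraclass correlation (ICC) as shown below.

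**1. Pooled r with no within-fetus tracking, many patients.** Acoustic reading = baseline + within-fetus change, with variance B + W.
- Flat ECG (returns the baseline only): r = √(B/(B+W)) = √(100/136) = 0.86. The within-fetus correlation is undefined because the ECG does not vary.
- Noisy ECG (baseline plus independent noise of variance W): r = B/(B+W) = 100/136 = 0.74. The true within-fetus correlation is 0.

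**2. The same with the five patients who decide.** Five baselines estimate the between-fetus spread poorly, and the coefficient is lower on average. By simulation at 10/6 bpm:

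| ECG | Mean pooled r | 95% of runs |
|---|---|---|
| Flat | 0.78 | 0.48 to 0.92 |
| Noisy | 0.62 | 0.22 to 0.86 |

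The limits move by a few hundredths between simulation runs.

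**3. Dependence on the SDs (noisy ECG).** With equal SDs of 10 bpm, r = 100/200 = 0.50 with many patients and about 0.40 on average with five. Over between-fetus SDs of 5 to 15 and within-fetus SDs of 3 to 10 bpm, the many-patient value runs from 25/125 = 0.20 to 225/234 = 0.96.

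**4. One value per patient.** For an observed r of 0.80, the Fisher interval is tanh(atanh 0.80 ± 1.96/√(n−3)). With n = 5 this is −0.28 to 0.99. If 50 readings (ten from each of the five) were counted as n, it would be 0.67 to 0.88.

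**5. Intervals on pooled readings.** For the mean device difference, the design effect is 1 + (m−1)·ICC, and its square root is the factor by which a naive interval is too narrow. For ICC 0.1 to 0.5:

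| Readings per patient, m | Design effect | Too narrow by a factor of |
|---|---|---|
| 10 (one per minute) | 1.9 to 5.5 | 1.4 to 2.3 |
| 40 | 4.9 to 20.5 | 2.2 to 4.5 |
| 600 (one per second) | 60.9 to 300.5 | 7.8 to 17.3 |

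This formula is for a mean difference, not for a correlation or an ROC curve. For the pooled correlation itself, simulation at SDs of 10 and 5 bpm with five patients shows that a nominal 95% interval covers about 58% at 10 readings per patient and about 30% at 40.

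**The case against.** The strongest reply is that the plan never says readings will be pooled. Comparing ten minutes of FHR woman by woman, and proceeding in steps of five patients, is compatible with a per-patient reading. That is correct, and a reader who infers that pooling is the plan goes further than the text. The gap remains, because a single per-patient value does not measure tracking and no within-patient analysis is named.

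A reader might also infer that the study will report intervals that count readings as patients. The documents plan no interval. The error arises only if someone computes one on pooled readings, and its size depends on a reading interval and an ICC that are not given. A factor of 8 to 17 needs one-second readings and concerns the mean device difference.

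A sensor that returns every baseline and misses every change is an extreme case with no basis in the documents. Real decelerations would increase the within-fetus spread and lower a pooled r, a flat trace beside a varying one could be seen by eye, and signal-noise ratio is a separate primary element. All of this is fair. The case shows what the coefficient fails to measure; it does not predict how the device behaves.

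Finally, a within-fetus analysis may have little to work on. Group 1 is not in active labor, and the plan anticipates no FHR abnormalities in the scheduled cesareans. This limits the remedy and should be stated in the plan. It does not favor a pooled coefficient.

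**Conclusion.** The point holds as a gap in the analysis plan that should be closed. Neither a pooled nor a one-value-per-patient correlation or ROC curve would show whether the ECG follows changes within a fetus, and the plan names nothing that would.

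Under the assumed SDs of 10 and 6 bpm, five patients with no tracking at all would on average give a pooled r of about 0.6 to 0.8, with wide spread from run to run. With no cut-off stated, values of that size could be taken as correlating. The size rests on between-fetus spread exceeding within-fetus spread, so the documents do not support saying that the pooled correlation must be high. Nor do they support a fixed factor for over-narrow intervals: only the direction is certain, and only for an interval computed on pooled readings as if they were independent.

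**What to change.** In 2.4.6.5:
- State the epoch over which paired readings are formed.
- Replace the correlation and ROC comparison with within-patient agreement: a repeated-measures Bland-Altman analysis, or a mixed model with a random patient effect that separates between-fetus from within-fetus variation.
- Base any interval on patients as the unit, using a small-sample t or model-based method. A percentile bootstrap is unsuitable at five patients: for a mean, a nominal 95% interval covers only about 83% in simulation.
- Show each patient's paired traces.
- State that paired data may contain few decelerations, so tracking of decelerations may remain untested.

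In 2.4.6, Group 2 item (b), base the decision on a per-patient agreement criterion fixed in advance (what agreement a patient must show, and how many of the five must show it), not on one pooled coefficient. Align the wording of 2.4.6.3 with this.

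No extra patients or measurements are needed. The cost is a little more analysis work, and intervals that will be wider than those from pooled readings.
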